### Treated Population

All patients in which the guidewire went through the sheath, even though if not all eligibility criteria were met or if a device failure occurred or if the clot could not be retrieved.

The primary safety endpoint will be determined on the Treated Population.

### Per-protocol Population

All patients from the Treated Population who comply to all eligibility criteria.

No separate analyses will be performed for the per-protocol population.

### Development Performance Population

This population includes patients from whom at least 1 acquisition was captured by the CSGS. Data of this population will be used during the development phase to build the different models for classification of RBC-positive and platelet-positive.

#### Local-Scale Performance Population

This population includes patients for whom data was collected by the CSGS during at least 1 tag in the clot based on expert labelling excluding patients from the Development Performance Population. Data of this population will be used during the validation phase to validate the model built during the development phase.

The analysis of the primary performance endpoint will be performed on data from the Local-Scale Performance Population. Performance assessment during the validation phase will be done only on tags in the clot.

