### 11.2 SECONDARY ENDPOINTS

The Secondary Endpoints are:

1. The concordance between aggregated occlusion measurements (**clot scale**) done by CSGS, and the histopathology results of the clot retrieved during the EVT procedure, regarding **red blood cell content** in the occlusion.
2. The ability of CSGS detecting the **proximal end of the occlusion** (sensor-scale), as compared to the physician's labelling (tag 'PRE-CLOT' for no occlusion contact and tag 'CLOT' for occlusion contact).
3. **Procedural success** defined as the ability to navigate CSGS to the occlusion site and measure electrophysiological properties of the occlusion.
4. The ability to perform binary classification of individual electrophysiological parameter measurements (**local scale**) by distinguishing local regions with substantial platelet content (**platelet-positive**) from regions with negligible platelet content (**platelet-negative**) in the occlusion.
5. The concordance between aggregated occlusion measurements (**clot scale**) done by CSGS, and the histopathology results of the clot retrieved during the EVT procedure, regarding **platelet content** in the occlusion.
6. The ability to perform binary classification of individual electrophysiological parameter measurements (**local scale**) by distinguishing local regions with substantial fibrin content (**fibrin-positive**) from regions with negligible fibrin content (**fibrin-negative**) in the occlusion.

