**Clinical investigation plan - CLOT OUT****15.2 ANALYSES POPULATION**

This study will be conducted in subjects presenting an acute ischemic stroke due to M1 occlusion, eligible for EVT based on neuro-interventionist and/or neurologist investigators' opinion.

Intention To Treat (ITT) Population

All patients who were enrolled, so all patients (or legally authorized representatives) who signed and dated the patient information consent form even though the CSGS was not used in the subject.

The **safety analysis** (amount of AE) will be performed on the intention to treat (ITT) population.

Treated Population

All patients in which the guidewire went through the sheath, even though if not all eligibility criteria were met or if a device failure occurred or if the clot could not be retrieved.

The **primary safety endpoint** will be determined on the Treated Population.

Per-protocol Population

All patients from the Treated Population who comply to all eligibility criteria.

No separate analyses will be performed for the per-protocol population.

Development Performance Population

This population includes patients from whom at least 1 evaluable acquisition was captured by the CSGS. An evaluable acquisition is defined as a "CLOT tag" or "Clot or beyond" tag with non-anomalous (see criteria section 15.6) impedance measurement. Data of this population will be used during the development phase to build the different models for classification of RBC-positive and platelet-positive.

Local-Scale Performance Population

This population includes patients for whom non-anomalous acquisition was collected by the CSGS during at least one tagged measurement with clot contact excluding patients from the Development Performance Population. Data of this population will be used during the validation phase to validate the model built during the development phase.

The analysis of the **primary performance endpoint** will be performed on data from the Local-Scale Performance Population.

Clot-Scale Performance Population

All patients from the Local-Scale Performance Population of which the clot could be retrieved for histological assessment.

Performance evaluation of the secondary performance endpoints related to the clot scale will be done on the Clot-Scale Performance Population.

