The single electrode pair measurement is defined as the response to an applied micro-current through an electrode pair. Such a response is referred to as 'the electrophysiological parameter': it depends on the arrangement and type of cells and interspersed biochemical components. The response across a single electrode pair is composed of a set of real numbers (up to 32 for CSGS) which are not independent; this set of numbers is referred to as a 'spectrum' since it forms the response as the micro-current frequency is swept across a pre-defined range. This is also referred to as a 'local-scale measurement'. A measurement triggered by the Cloviz software collects at a given time point the spectrums from a pre-defined set of electrode pairs. This is also referred to as a 'sensor-scale measurement' since it sweeps the electrode pairs of the sensor.

The CSGS will be inserted and up to 6 measurements will be done: 1 measurement distal to the access catheter in circulating blood (this is the reference measurement), 1 measurement proximal to the site of occlusion, 2 to 3 measurements inside the occlusion and 1 measurement at the most distal advancement of the guidewire (ideally distal to the occlusion). The collection of measurements made in contact with the clot is referred to as the 'clot-scale' measurement.

[figure not shown]

Figure 1: Schematic view of the sensor presenting the different scales of measurements.

Data from the CSGS is synced to the cloud database. These data are processed offline. Individual electrophysiological measurements are annotated manually by Sensome experts by inspecting the signal and the histological content from the full clot.

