#### d) Tertiary Endpoints

There are 6 tertiary more exploratory endpoints. The tertiary endpoints assess the correlation between the CSGS measurements with intervention parameters such as:

1. Arterial wall detection for individual measurement - The local detection of arterial wall vs. clot when clot-contact is ensured. Differentiation of the arterial wall cannot be validated by external means. Expert labelling will be done on tagged acquisitions (PRE CLOT, CLOT, CLOT or beyond, MOST DISTAL): for each electrode pair the expert will evaluate whether it is in contact with arterial wall or not. Comparison with the prediction model will be made at such local-scale (single electrode pair) by using the same performance metric as for the primary endpoint, i.e. by means of the AUC of ROC.
2. The ability of CSGS detecting the distal end of the occlusion. Two comparisons will be made: one with expert labelling on tagged acquisitions and one compared to external evaluation when distal injection of contrast agent allowed the core lab to evaluate the positioning. The expert will label the CLOT, CLOT or beyond, and MOST DISTAL tagged acquisitions as whether the sensor is in clot contact or not. The last clot contact will be used as the positive example and the first labelled non-contact measurement will be used as the negative example. Regarding the subset of interventions for which a distal injection of contrast agent allowed the identification of the location of the sensor in or behind the clot by the imaging core lab, the ground truth will be used identically on the last tagged acquisition in the clot and the first tagged acquisition where the sensor is established behind the clot. The AUC of ROC will be used identically that for the Secondary endpoint for the proximal detection. Data from the interventions in the development and validation sets will be the same as for the primary endpoint.
3. The number of passes - The prediction of the number of passes to remove the clot. Interventions with successful clot retrieval are used. The input may include all the electrophysiological measurements of the intervention. The output is the number of passes needed to remove the clot as reported by the investigator. Data from the interventions in the development and validation sets will be the same as for the primary endpoint.

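### Protocol and SAP define the primary performance set differently, and the SAP's expert in-clot decision has no criteria, masking or freeze point after model lock

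*SAP*

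**What the plan says.** Protocol 15.2 puts a patient in the Local-Scale Performance Population if "non-anomalous acquisition was collected by the CSGS during at least one tagged measurement with clot contact", and excludes patients used for development. In the same section, under the Development Performance Population, it ties evaluability to the tag placed in the procedure: "An evaluable acquisition is defined as a 'CLOT tag' or 'Clot or beyond' tag with non-anomalous" measurements. Protocol 11.2 (item 2) treats these tags as the physician's labelling: "tag 'PRE-CLOT' for no occlusion contact and tag 'CLOT' for occlusion contact".

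SAP 8.b defines the same population by data collected "during at least 1 tag in the clot based on expert labelling". It then adds: "Performance assessment during the validation phase will be done only on tags in the clot".

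The experts are the sponsor's. SAP 4.b says that individual measurements are "annotated manually by Sensome experts by inspecting the signal and the histological content from the full clot". Protocol 15.7 and SAP 7 say that independent reviewers cannot do the RBC classification, and they keep annotators away from incoming validation data until the models are fixed. The two-expert-plus-third rule given there covers the RBC-positive/negative label. SAP 8.c.i locks the model for the validation phase. Protocol 15.3 and SAP 8.c.i both state that the evaluation approach is free of optimistic bias.

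**The concern.** The two documents give different rules for what enters the primary performance analysis, although the SAP's change history says that version 2 was updated to match protocol version 6. Neither document explains the difference.

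Under the SAP wording, a sponsor expert's view of whether a tag lies in the clot decides whether its readings count. That decision falls after the model is locked, and nothing specified constrains it. Separating development from validation data protects against overfitting. It does not protect against choosing test readings once the model exists. If that choice were related to how easily a reading is classified, the AUC would move without any change in the device. If it removed many tags, the CI would also be wider than planned.

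**Working it through.** **Step 1: the two rules side by side.**

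| Feature | Protocol 15.2 | SAP 8.b |
|---|---|---|
| Unit that qualifies a patient | Tagged measurement with clot contact | Tag in the clot |
| Who decides contact | Not stated; the tag is the physician's (11.2) | Expert labelling |
| Anomaly condition | In the definition | Not in the definition; the exclusions are in 8.c.vi |
| Readings scored | Not limited further | Only tags in the clot |

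Neither document gives criteria, a number of readers, masking or a freeze point for the in-clot decision. The only sensitivity analysis planned (Protocol 15.6, SAP 8.c.xviii) concerns the safety endpoint.

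**Step 2: reproduce the planned precision.** Inputs from Protocol 15.5 and SAP 6: AUC A = 0.85, 5.44 independent readings per tag, 3 clot-contact tags per intervention, 53% RBC-positive and 47% RBC-negative, 95% CI width at most 0.10.

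Hanley–McNeil: Q₁ = A/(2−A) = 0.85/1.15 = 0.7391; Q₂ = 2A²/(1+A) = 1.445/1.85 = 0.7811; A² = 0.7225.

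SE² = [A(1−A) + (n₊−1)(Q₁−A²) + (n₋−1)(Q₂−A²)]/(n₊n₋), and width = 2 × 1.96 × SE.

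- 13 interventions: 13 × 3 × 5.44 = 212.2 readings (112.4 positive, 99.7 negative); width 0.1031.
- 14 interventions: 14 × 3 × 5.44 = 228.5 readings (121.1 positive, 107.4 negative); SE 0.0254; width 0.0994.

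So 14 is the smallest number that meets the limit. The total is (11 + 14)/0.60 = 41.7, rounded up to 42. Both of the plan's figures reproduce.

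**Step 3: precision if expert selection removes tags.** With 14 interventions and an assumed number of tags kept:

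- 2.5 tags each: 190.4 readings, width 0.109.
- 2 tags each: 152.3 readings, width 0.122. Restoring 0.10 would take 21 validation interventions, for a total of (11 + 21)/0.60 = 53.3, rounded up to 54.

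**Step 4: possible shift in the AUC, as an illustration.** Scores are simulated as equal-variance binormal with separation √2 × Φ⁻¹(0.85) = 1.466, 53% positive and 5 readings per tag. The most ambiguous tags are dropped. The drop shares are assumptions, because the documents give none.

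| How ambiguity is ranked | Labels within a tag | Drop 10% | Drop 20% |
|---|---|---|---|
| Mean distance of readings from the midpoint | Mixed | 0.86 | 0.87 |
| Mean distance of readings from the midpoint | Single | 0.86 | 0.87 |
| Distance of the tag mean from the midpoint | Mixed | 0.853 | 0.855 |
| Distance of the tag mean from the midpoint | Single | 0.88 | 0.90 |

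The table assumes that the in-clot decision ranks tags exactly by RBC-score ambiguity. With a correlation of 0.3 between the two, the AUC is about 0.855 at 10% and 0.858 at 20%. A random 20% drop leaves it at 0.850.

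**The case against.** The strongest reply is that the SAP fills a gap in the protocol. A 'Clot or beyond' tag does not establish contact, the protocol names nobody to confirm it, and Protocol 15.1 leaves further detail to the SAP. The endpoint concerns regions in the occlusion, so removing readings taken beyond it is proper. This stands. It justifies having an in-clot rule, and it is why every tag should not simply become primary. It does not supply the missing criteria, readers, masking or freeze.

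A reader might also infer four stronger things that the documents do not support:

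- **That the experts are unblinded and choose tags from the signal.** No document says they see model scores. The signal-and-histology wording in SAP 4.b concerns annotation of individual measurements, and the basis of the in-clot decision is not stated. The instruction "The expert will label the CLOT, CLOT or beyond, and MOST DISTAL tagged acquisitions as whether the sensor is in clot contact or not" belongs to tertiary endpoint 2 (the distal end of the occlusion). It shows that experts re-label physician tags there, not that the same rule governs the primary set.
- **That the SAP abandons the anomaly filter.** The word is missing from its population definition, but SAP 8.c.vi keeps all four exclusion rules.
- **That hard readings will be removed and the AUC inflated.** Expert labelling could also remove readings properly, or add some, such as from MOST DISTAL tags.
- **That the shift would reach 0.05, half the planned CI width.** That needs one label per tag, ranking by the tag mean, a 20% drop and a perfect link to ambiguity, all together.

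**Conclusion.** The point holds as a conflict between the documents and a missing control, not as demonstrated bias. Protocol 15.2 and SAP 8.b give different primary performance sets. Under the SAP, readings can leave or enter that set after model lock at the discretion of sponsor staff. The stated freedom from optimistic bias is therefore not secured for the choice of readings.

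The most stable illustration is a rise of about 0.01 to 0.02 from an AUC of 0.85. The full range runs from no change, if the decision is unrelated to the RBC score, to 0.90 in the extreme case. All of these rest on assumed drop shares of 10–20% and a binormal model. The loss of precision depends only on how many tags remain, using the plan's own formula: at 2 tags per intervention the width exceeds the plan's limit by about a fifth (0.122 against 0.10). No stated sample-size figure is wrong.

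**What to change.** Reconcile Protocol 15.2 and SAP 8.b to one definition of the population and of the readings scored. If expert in-clot selection stays primary:

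1. Write the in-clot criteria into the SAP, and apply them through the existing two-expert-plus-third process, with the readers masked to model scores.
2. Freeze the list of included readings, after the Protocol 15.6 anomaly filter, before any validation score is generated.
3. Report how many tags and patients the experts removed or added, with reasons.
4. Add a sensitivity AUC on all non-anomalous CLOT and 'Clot or beyond' tags as placed in the procedure.

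The cost is wording in two documents, slightly more analysis work, and possibly a less favourable sensitivity figure. No extra patients or data are needed for these changes.

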#### Clot-Scale Performance Population

All patients from the Local-Scale Population of which the clot could be retrieved for histological assessment.

Performance evaluation of the secondary performance endpoints related to the clot scale will be done on the Clot-Scale Performance Population.

Reasons why patients did not undergo the study procedure with the study devices will be listed. A listing will give an overview if patients were involved in a specific population set.

## c) Statistical analysis methods

### i. Statistical Procedures

A major objective of this study is to evaluate the prediction model(s) of the Clotild® Smart Guidewire System. These prediction models are based on physical properties of the impedance measurements captured by the sensor, complemented with a comparison to suitable labels for each endpoint (a.k.a. phenomenological modelling). The impedance dataset that will be constructed during the clinical investigation should serve to develop the prediction models (model development) and to evaluate their prediction accuracy (model evaluation). Such an evaluation methodology is inspired from Good Machine Learning Practice for Medical Device and avoids any optimistic bias.

Given the necessity to isolate a validation set free of any model optimization to obtain unbiased generalization scores, the dataset will be split into two pieces:

1. **The development dataset**, where model optimizations is being made to arrive at a single particular model trained on the full development dataset.
2. **The validation dataset** that is solely used to assess the performance of the model.

#### **Development dataset**

Data of the first interventions will be included in the development dataset. These data will be used so that the model can be fully determined before further patients are enrolled in the validation dataset.

In order to develop the prediction model(s), data from the development dataset are analysed on an ongoing basis.

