**Clinical investigation plan - CLOT OUT****15.6 MISSING DATA**

To assess the possible impact of missing data on the primary safety endpoint a sensitivity analysis will be conducted. Given the primary safety variable is a binary variable it is rather straightforward to assess the impact of different assumptions. In a worst case scenario all missing data are considered failures which will lead to the worst case scenario estimator of the proportion of perforations/dissections.

Regarding the impedance measurements captured by the CSGS, data might be missing or anomalous, having an impact on the performance endpoints. Based on the Device Deficiency rate obtained in the first 31 treated subjects, the estimated amount is 40%. This missingness/anomaly might be due to the following reasons:

- Technical malfunctions, leading to missing data or anomalous data, among which:
  - device anomaly caused by manufacturing anomaly
  - device anomaly due to electrical connection loss during navigation
- Use error, leading to:
  - missing data because measurements have not been tagged
  - anomalous data because the sensor was covered by the microcatheter while the measurement was tagged, as confirmed by the Imaging Core Lab on the angiography images corresponding to the tagged measurement.

The criteria to discard anomalous measurements due to technical malfunction include:

- Any acquisition associated with an error code raised by transmitter software (for instance due to loss of communication between sensor and transmitter) will be excluded from the development and validation datasets.
- Electrophysiological measurement from an electrode pair that shows a constant raw digital signal across acquisition frequencies (constant or piecewise constant with a single step) is considered anomalous and will be excluded.
- Electrophysiological measurement from an electrode pair that shows digital saturation consistently from REFERENCE to PRE-CLOT is considered anomalous; all remaining measurements made with this electrode pair will be excluded from the datasets.
- Anomalies related to invalid reference measurements are reported as too-high dispersion across electrode pairs in the 'REFERENCE' measurement. Persistence of the anomaly up to the 'PRE CLOT' measurement requires exclusion of all measurements from the concerned electrode pairs.

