**15.7 BIAS**

To minimize bias, an independent Data Safety Monitoring Board (DSMB) (see section 20.3) will be responsible for monitoring safety and performance aspects of the study. The DSMB consists out of an uneven number of experts in the field, enabling the assessment and conclusion with majority votes. If needed, the DSMB may invite ad hoc team members, such as statistical support. These ad-hoc members will refrain of voting. To review safety events happening in the study – for some events, the DSMB may be requesting additional information from the investigational site or the core lab to allow a comprehensive review. DSMB will be responsible of adjudicating the primary safety endpoint.

Secondly, to evaluate the Primary Performance Endpoint a binary classification of individual electrophysiological parameter measurements into 'RBC-positive' and 'RBC-negative' is performed by 2 SENSOME experts independently. In case of discrepancies, a 3rd expert will decide on the classification. This process cannot be performed by independent reviewers. Following SENSOME's internal procedure (SEN\_QAS\_SOP\_1010), experts involved in annotating data shall not inspect the incoming validation dataset before the development is declared finished (the prediction models being fixed). As dataset inspection is also routine to detect anomalies, another SENSOME expert not involved in the development could be designated in the transition period (when the development phase is not terminated but the development set is completed).

Thirdly, an expert in the field of histopathology from an independent Core Lab (Mayo Clinic) will perform the histopathological analysis of the clots. The core lab will be blinded for the results of the CSGS. Rules of operation and responsibilities are outlined in the Core Lab Instructions.

Fourthly, another independent core lab (UCLA) will check the images. The imaging Core Lab will be set-up by 2 experienced readers. Both will check independently the pre-procedural, procedural and post-procedural images. Both readers will assess the primary safety endpoint. In case of disagreement between the 2 readers, a decision will be made by consensus. Rules of operation and responsibilities are outlined in the Core Lab Instructions.

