### Development set size

The development set size was fixed to obtain a near-optimal RBC categorization performance (as defined in the primary performance endpoint), based on preliminary research performed by SENSOME on an ex-vivo dataset (DND\_tr-0033-clot-composition-phenomenological-model-development\_v1). The standard approach at Sensome was to use machine learning techniques to cope with the complexity of the signal. However, our accumulated experience guided the design of a phenomenological model (based on observations and on physical properties of the signal). Its performance on local-scale composition prediction, evaluated on the ex-vivo dataset, is comparable to the machine learning model performance previously developed. The fine-tuning of its parameters has got only a minor influence on the performance, as assessed on the ex-vivo dataset.

Its extrapolation for thrombectomy-like procedures requires an additional rule to distinguish the arterial wall and potentially a fine-tuning of handful of its parameters. Overall, the number of examples needed to complete the first local-scale clot composition prediction model is constrained by the observation of ideal cases (locally pure RBC content and locally pure platelets content). Based on the fraction of pure cases that was observed on the ex-vivo data set, and on rules to sub-sample this data set regarding the number of clot contact measurements per intervention, we find that  $N = 11$  is an adequate estimate of the development sample size.

We thus require a number of  $N_D = 11$  interventions with at least 1 evaluable measurement in contact with the clot to be included in the development set to reach near optimal performance with respect to primary performance endpoint assessment (Development Performance Population).

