### Validation set size

The minimum number of  $N_V$  interventions to be included in the validation dataset to estimate the performance  $\hat{A}$  with sufficient statistical confidence margin is determined, with  $\hat{A}$  the area under the ROC curve (AUC) of the prediction model obtained on the validation sample of the population.

The following assumptions are made:

- **Estimated average number of independent individual measurements from a single tagged acquisition with clot contact = 5.44** (based on the quality check of data collected in the first 9 procedural successes)

- **Estimated average number of tagged acquisitions with clot contact per intervention = 3** (based on the quality check of data collected in the first 9 procedural successes)
- **Estimated number of RBC-positive cases = 53%** (based on the quality check of data collected in the first 9 procedural successes)
- **Expected number of RBC-negative cases = 47%**
- **An AUC of 0.85 is assumed with a maximal width of 0.1 for the 95% confidence interval**

With these assumptions, using the Hanley and McNeil estimate (Hanley and McNeil 1982) for the confidence interval to reach an expected AUC of 0.85 and a maximal width of the 95% confidence interval of 0.1, a number of  **$N_v = 14$  interventions** with at least 1 evaluable measurement valid interventions are necessary for the validation set (Local-Scale Performance Population).

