### **Validation dataset**

After completion of the development phase, data of the following interventions will be used in the validation dataset. The validation dataset shall be used to assess the generalization performance of the model(s) developed during the development phase. When moving to the validation stage, all steps used from input data, i.e. individual impedance spectrums for each electrode pair, to the score prediction shall be fully determined. When moving to the validation phase the model(s) shall be locked, remaining unchanged during the course of the validation phase.

This same procedure of splitting the dataset into two sets (development dataset and validation dataset) will be performed for the primary performance endpoint assessment as well as for the secondary and tertiary endpoint assessments.

Confidence intervals will be computed with the bootstrap.

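### The rules that split patients into development and validation are defective: the development population has no number or order limit, and patients treated before the model lock have no clear assignment

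*SAP*

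**What the plan says.** **Order of the split.** SAP 8.c.i assigns the first interventions to development and adds: "These data will be used so that the model can be fully determined before further patients are enrolled in the validation dataset". On validation it says: "After completion of the development phase, data of the following interventions will be used in the validation dataset". The models are to be locked on moving to validation (protocol 15.3, SAP 8.c.i).

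**Transition period.** Protocol 15.7 and SAP 7 both speak of an incoming validation dataset that certain experts may not inspect until the models are fixed. Both allow another sponsor expert to check for anomalies in a transition period, described as the time "when the development phase is not terminated but the development set is completed".

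**Populations.** Protocol 15.2 defines the Development Performance Population: "This population includes patients from whom at least 1 evaluable acquisition was captured by the CSGS". SAP 8.b has: "This population includes patients from whom at least 1 acquisition was captured by the CSGS". Neither definition gives a number or an order. In both documents the Local-Scale Performance Population, on which the primary performance endpoint is analysed, excludes patients in the Development Performance Population.

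**Sizes.** Protocol 15.5 and SAP 6 require 11 evaluable interventions for development and 14 for validation. The precision target for the latter is: "An AUC of 0.85 is assumed with a maximal width of 0.1 for the 95% confidence interval". The total is (11 + 14)/0.60 = 42. Protocol 15.6 gives the basis of the 0.60: "Based on the Device Deficiency rate obtained in the first 31 treated subjects, the estimated amount is 40" per cent.

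**The concern.** The split decides who enters the primary performance AUC, and two of its rules fail.

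First, the set definitions cancel each other. A patient cannot have usable clot data without also meeting the definition of the development population, and meeting that definition removes the patient from validation.

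Second, a patient treated after the development set is full but before the model is locked is outside validation under SAP 8.c.i and inside it under SAP 7 and protocol 15.7. At least 31 subjects had been treated when the current protocol and SAP were written, so this window may contain a material share of the evaluable cases.

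The claim in protocol 15.3 and SAP 8.c.i that the method is free of optimistic bias depends on a cut fixed independently of the data. The stated precision depends on how many evaluable patients fall on the validation side of that cut.

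**Working it through.** **1. Reproduce the plan's figures.** Inputs from protocol 15.5 and SAP 6: AUC A = 0.85; 5.44 independent measurements per acquisition; 3 clot-contact acquisitions per intervention; 53% RBC-positive and 47% RBC-negative.

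- Measurements per intervention: 3 × 5.44 = 16.32.
- Hanley–McNeil: SE² = [A(1−A) + (n₊−1)(a−A²) + (n₋−1)(b−A²)]/(n₊n₋), with a = A/(2−A) = 0.7391, b = 2A²/(1+A) = 0.7811 and A² = 0.7225.
- At 14 interventions: n = 228.5, n₊ = 121.1, n₋ = 107.4. The numerator is 0.1275 + 120.1 × 0.01663 + 106.4 × 0.05858 = 8.36. SE = √(8.36/13,004) = 0.02535, and the full width is 2 × 1.96 × SE = 0.0994.
- At 13 interventions the width is 0.1032, so 14 is the minimum.
- Total: 25/0.60 = 41.7, rounded up to 42.

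Both stated figures reproduce.

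**2. Apply the population definitions literally.**

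- *SAP 8.b.* Validation needs data from at least one tag in the clot. Such a patient necessarily has at least one acquisition, so belongs to the development population and is excluded. Validation contains 0 patients.
- *Protocol 15.2.* An evaluable acquisition is a non-anomalous one carrying a clot tag or a clot-or-beyond tag. The only patients left for validation are those whose sole non-anomalous clot-contact acquisition carries some other tag. That is close to nobody.
- The SAP definition also omits the evaluability requirement, so the two development populations are not the same set.

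**3. Effect of the lock point if SAP 8.c.i is applied as written.** Neither document gives the date of the lock or the number treated at that time, so a range is needed. Assumptions: all 42 enrolled patients are treated, and 60% are evaluable throughout. Expected evaluable validation cases = (42 − number treated at lock) × 0.60.

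| Treated at lock | Treated after lock | Expected evaluable | CI width |
|---|---|---|---|
| 18 | 24 | 14.4 | 0.099 (at 14) |
| 19 | 23 | 13.8 | 0.099 (at 14) |
| 22 | 20 | 12.0 | 0.107 |
| 25 | 17 | 10.2 | 0.118 (at 10) |
| 28 | 14 | 8.4 | 0.132 (at 8) |
| 31 | 11 | 6.6 | 0.145 (0.141 at 7) |

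The first two rows correspond to locking as soon as the 11th evaluable case is reached: 11/0.60 = 18.3 treated. In the last row, even with no anomalies, 11 interventions give a width of 0.112, above the target. Reaching 14 evaluable after a lock at 31 would take 31 + 14/0.60 = 54.3, so 55 treated.

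**4. Size of the ambiguous group.** Of the first 31 treated, 31 × 0.60 = 18.6 are expected to be evaluable. Beyond the 11 for development that leaves 7.6. If the lock came at 31 or later, these 7 to 8 patients are the ones whose assignment depends on which sentence is followed.

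**The case against.** The strongest reply is that the plan, read as a whole, makes its intent clear. Protocol 15.5 and SAP 6 attach the name Development Performance Population to 11 evaluable interventions and the name Local-Scale Performance Population to 14. SAP 8.c.i says the first interventions go to development. Together these give the first 11 evaluable interventions, so the empty set follows only from reading one definition alone. That stands as evidence of intent. It does not repair the definitions, which are what an analyst would program.

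On the lock, SAP 8.c.i can be read as letting validation data accrue while barring their use until the model is fixed. That reading fits the transition text and keeps 14 attainable. It is a reasonable reading but not the only one, since the section also ties entry to validation to a model already determined. The bar on inspection in protocol 15.7 and SAP 7 is a real safeguard, although neither section asks for a dated access record or mentions access to histology.

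A reader might infer more than this in three ways, and the documents do not support any of them:

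- *That only about 7 validation cases remain.* Both documents say the model needs a further rule for the arterial wall and possibly some tuning, while reporting 31 treated subjects. That sentence explains why in-vivo development cases are needed; it is not a dated status report, and no section says the model was still open at subject 31.
- *That the SAP forbids what the protocol allows.* The transition provision is in both documents, so the conflict lies within the SAP as well.
- *That the sponsor has chosen, or will choose, the cut after seeing data.* The documents leave room for this but do not show it.

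Whether 42 patients will yield 25 evaluable ones is a separate attrition question and is no evidence about the split.

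**Conclusion.** Two defects in the stated rules are established. The development population lacks the number and order limits that the sample size section assumes, which leaves the validation set empty under the SAP as written and essentially empty under the protocol. Patients treated between completion of the development set and the model lock have no unambiguous assignment.

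The numerical consequence is conditional. Under lock-first, expected evaluable validation interventions run from about 14 (width 0.099, the plan as sized) if the lock came at 18 to 19 treated, down to about 6.6 to 7 (width 0.145 to 0.141) if it came after subject 31, and lower if later still. If patients from the transition period count, the planned 14 is not affected by the lock point.

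These figures rest on the plan's own formula with its independence assumption, a constant 60% evaluable rate, and 42 treated. Any enrolled but untreated patient would lower them. Because the rules determine the analysis set for the primary performance endpoint, they should be corrected before the validation data are analysed.

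**What to change.** Use one rule in both documents:

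- **Development:** the first 11 treated patients, by procedure date and time, with at least one evaluable clot-contact acquisition.
- **Validation:** every later evaluable patient whose impedance and histology data were kept from the model developers until a dated model lock, whether treated before or after that lock.
- **Alignment:** reword SAP 8.c.i to match the transition provision in SAP 7 and protocol 15.7, and restore the evaluability requirement in the SAP's development population.
- **Record:** state the lock date and the number of patients treated at that date, and keep a data-access log.
- **Fallback:** if quarantine of pre-lock patients cannot be documented, move them to development and restate the validation size and confidence interval width for the number actually remaining.

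The cost is wording in two documents plus a lock and access record. No additional patients are needed to apply the rule. Under the fallback, the stated precision may become less favourable.
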